1.1 Protocol Amendment: Summary of Changes

Previous Protocol Versions

Protocol	Date
Original	23 January 2015
Amendment 1	21 May 2015
Administrative Change 1	27 October 2015
Amendment 2	28 March 2016
Amendment 3	15 November 2016
Administrative Change 2	16 March 2017

The purpose of this amendment is to:

- Change the study Reference Safety Information (RSI) from the Duodopa Summary of Product Characteristics (SmPC) to the Levodopa-Carbidopa Intestinal Gel (LCIG), (also known as Duopa or Duodopa) Investigator Brochure (IB).

Rationale: *This change was made to align the study with AbbVie's Standard Operating Procedures (SOPs).*

Throughout the protocol changes were made to update language per the new protocol template, correct typographical errors, and provide clarity.

An itemized list of all changes made to this protocol under this amendment can be found in [Appendix E](#).

1.2 Synopsis

AbbVie Inc.	Protocol Number: M12-927
Name of Study Drug: Levodopa-Carbidopa intestinal gel (SLV-187)	Phase of Development: 3b
Name of Active Ingredient: Levodopa-Carbidopa	Date of Protocol Synopsis: 31 May 2017

Protocol Title: An Open-label, Randomized 26-Week Study Comparing Levodopa-Carbidopa INteStInal Gel (LCIG) Therapy to Optimized Medical Treatment (OMT) on Non-Motor Symptoms (NMS) in Subjects with Advanced Parkinson's Disease – INSIGHTS Study
	

Objectives:
 
Primary The primary objective of this study is to examine the effect of LCIG relative to that of OMT on non-motor symptoms associated with advanced Parkinson's disease (PD) as assessed by the Non-Motor Symptoms Scale (NMSS) Total Score and the Modified Parkinson's Disease Sleep Scale (PDSS-2) Total Score.
 
Secondary To assess the effect of LCIG relative to that of OMT on the motor symptoms/motor complications, safety, tolerability and health-related outcome measures.
 
Motor symptoms/motor complications will be measured by:
 
 • Unified Parkinson's Disease Rating Scale (UPDRS) Parts III and IV 
Safety and tolerability will be assessed by:
 
 • Adverse event monitoring • Neurological exams • Clinical laboratory evaluations • Electrocardiogram • Vital signs and weight • Columbia Suicide Severity Rating Scale (C-SSRS) • Minnesota Impulsive Disorders Interview (MIDI) • Sleep Attacks Questionnaire (SAQ) 
Health Related Outcomes will be measured by:
 
 • Parkinson's Disease Questionnaire-8 (PDQ-8) • Clinical Global Impression of Change (CGI-C) • UPDRS Parts I and II • Patient Global Impression of Change (PGIC) • Parkinson Anxiety Scale (PAS) • Geriatric Depression Scale (GDS-15) • King's Parkinson's Disease (PD) Pain Scale 	
Investigators: Multi-center	

Study Sites: This study will be conducted at approximately 40 – 50 sites in approximately 10 countries worldwide

Study Population:

Levodopa-responsive Parkinson's disease patients with severe motor fluctuations and hyperkinesia/dyskinesia when available combinations of Parkinson medicinal products have not given satisfactory results.

Number of Subjects to be Enrolled: Approximately 88 subjects (44 per each treatment group)

Methodology:

[figure not shown]

Figure 1: Study Design Schematic

This is a Phase 3b, open-label, randomized multicenter 26-week study comparing LCIG to optimized medical treatment (OMT). The study will consist of 3 sequential periods: Screening, Treatment and Follow-Up. The OMT group will have the same schedule of visits/procedures throughout the study as the LCIG group except for visits related to NJ/PEG procedures and titration of LCIG.

Methodology (Continued):

The Screening Period (V1 – V3)

The Screening Period will be the same for all subjects screened into the study. The Screening Period will consist of three visits, Visit 1 (V1), Visit 2 ([V2] [optional]) and the Randomization Visit (V3) in which the subject will be assessed to determine eligibility. A movement disorder specialist should perform an interview of the subject at screening. The duration of the Screening Period can be between 30 – 67 days to accommodate the required procedures, training and collection of diaries, and allow for stabilization of anti-PD medications and medications to treat NMS. All anti-PD medications and any other medications used to treat individual non-motor symptoms (e.g., Insomnia, depression, anxiety), must be stable with no adjustments to the frequency of administration, dose of administration or total daily dose. Both anti-PD medications and medications to treat NMS are required to be stable for a minimum of 30 days. During the Screening Period, no study drug (LCIG) will be administered. Visit 2 is optional and is based on the PI's discretion of individual subject need during stabilization of anti-PD medications and medications to treat NMS. Subjects who are deemed eligible by randomization criteria at Visit 3 will be randomized at the end of Visit 3 to receive LCIG or continue on OMT following baseline assessments.

Treatment Period (V4 – V8)

OMT Group:

Those subjects randomized to continue OMT will remain on their current optimized regimen and will have study visits at the end of Weeks 2, 6, 12, and 26 following randomization (V3). The OMT group will not have a V4 (NJ/PEG-J Placement). The day after randomization (V3) will be considered Day 1 of their treatment period.

During the treatment phase, changes to anti-PD and NMS medications should remain stable and can only be made if medically indicated. Changes to the OMT arm can be made "if medically justified," not only for serious safety reasons.

LCIG Group:

In accordance with the LCIG approved Product Label for countries participating in the study, those subjects randomized to LCIG must discontinue all other anti-PD medications (e.g., dopamine agonists, COMT-inhibitors, amantadine, MAO-B inhibitors, anti-cholinergics, and subcutaneous apomorphine etc.) prior to LCIG initiation on Day 1 (V4); these medications should be tapered off according to the prescribing information and the discretion of the Investigator. With the exception of continuous subcutaneous delivery of apomorphine or levodopa containing formulations, these medications may be restarted if indicated by the subject's individual condition, but not within the first 28 days after LCIG initiation.

For those subjects randomized to LCIG, an optional, temporary nasojejunal (NJ) tube may be used initially to titrate the dose of LCIG. Following the NJ phase, a percutaneous endoscopic gastrostomy with a jejunal tube (PEG-J) will be performed by a gastroenterologist proceduralist. Total time to titration via the NJ and PEG-J should not exceed 14 days. Alternatively, subjects may proceed directly to placement of the permanent PEG-J tube without the NJ phase at the discretion of the principal investigator. If the subject proceeds directly to PEG-J, titration should be completed within 7 days. However, at the PI's discretion additional days of optimization may be made if indicated. Subjects on LCIG will return for study visits at the end of Weeks 2, 6, 12, 26 and 27 following PEG-J placement.

Methodology (Continued):

LCIG Group (Continued):

Subjects and/or caregivers must come into the clinic or pharmacy between V7 (Week 12) and V8 (Week 26) for clinical LCIG return and supply visits so that there is no risk of medication expiring. The drug dispensing visits will occur at Weeks 17 and 22 (\pm 7 days). Other assessments may be completed during these visits if required.

During the treatment phase, medications used to treat specific non-motor symptoms must remain stable for the duration of the study unless medically warranted.

Study Follow-Up

The OMT subjects will not have a follow-up visit (V9).

For LCIG subjects who elect to discontinue LCIG and not continue with commercially available product, a V9 will be conducted one week after NJ/PEG-J removal and the follow-up period will be up until 30 days after NJ/PEG-J removal. For LCIG subjects who will transition to commercial product, the SAE/AE follow-up period will be 30 days after conversion to commercial.

Diagnosis and Main Criteria for Inclusion/Exclusion:

Main Inclusion:

1. Subject must have a diagnosis of idiopathic Parkinson's disease according to the United Kingdom Parkinson's Disease Society (UKPDS) Brain Bank Criteria. See Appendix C for UKPDS.
2. Subject demonstrates persistent motor fluctuations in spite of individually optimized treatment.
3. The subject's Parkinson's disease is levodopa-responsive.
4. Subject has had optimal treatment with available anti-PD medication and their motor symptoms are judged inadequately controlled on this optimized treatment. Optimized treatment is defined as the maximum therapeutic effect obtained with pharmacological antiparkinsonian therapies when no further improvement is expected regardless of any additional manipulations of levodopa and/or other antiparkinsonian medication. This will be based on the Investigator's clinical judgment.
5. Subject and/or if applicable, their care-partner must be able to complete the Subject Dosing Diary and must be able to demonstrate the ability to operate, manipulate and care for the infusion pump and tubing.
6. Subject is eligible to transfer to commercial treatment of Duodopa after completing the study based on local country requirements.
7. Subject must have a minimum PDSS-2 total score of 18 at Baseline assessment.*
8. Subject must be able to understand the nature of the study and has had the opportunity to have any questions answered. Prior to the conduct of any study procedures (including any changes occurring in the subject's current therapeutic regimen), the subject, if judged by the PI to have decision making capacity, must have voluntarily signed the Independent Ethics Committees/Institutional Review Board (IEC/IRB) approved Informed Consent. In the absence of subject's ability to provide the informed consent, the informed consent must have been signed by a person who has the legal right to act on behalf of the subject following national laws
9. Male or female subjects at least 30 years of age.

Diagnosis and Main Criteria for Inclusion/Exclusion (Continued):

Main Inclusion (Continued):

10. If female, subject must be either postmenopausal, OR permanently surgically sterile OR for Women of Childbearing Potential practicing at least one protocol specified method of birth control, starting at Study Day 1 through at least 30 days after the last dose of study drug.
If the male subject is sexually active with female partner(s) of childbearing potential, he must agree, from Study Day 1 through 4 weeks after the last dose of study drug, to practice the protocol specified contraception.
 11. Females of childbearing potential must have a negative serum pregnancy test result at Screening, and a negative urine pregnancy test at Study Day 1.
 12. Females of non-childbearing potential (either postmenopausal or permanently surgically sterile as defined above) at Screening do not require pregnancy testing.
- * If previously excluded because of this inclusion criterion, subject is eligible to re-screen.

Main Exclusion:

A subject will not be eligible for study participation if he/she meets any of the following criteria:

1. Subject's PD diagnosis is unclear or there is a suspicion that the subject has a parkinsonian syndrome such as secondary parkinsonism (e.g., caused by drugs, toxins, infectious agents, vascular disease, trauma, brain neoplasm), parkinson-plus syndrome (e.g., Multiple System Atrophy, Progressive supranuclear Palsy, Diffuse Lewy Body disease) or other neurodegenerative disease that might mimic the symptoms of PD.
2. Subject has undergone neurosurgery for the treatment of Parkinson's disease.
3. Subject has discontinued apomorphine continuous infusion for the treatment of Parkinson's disease less than 3 months prior to screening visit.
4. Subject has any neurological deficit that might interfere with the study assessments (e.g., hemiparesis).
5. Known hypersensitivity to levodopa, carbidopa or radiopaque material.
6. Subject has contraindications to levodopa, (e.g., narrow angle glaucoma, malignant melanoma).
7. Subject experiencing clinically significant sleep attacks or clinically significant impulsive behavior (e.g., pathological gambling, hypersexuality) at any point during the three months prior to the Screening evaluation) as judged by the Investigator.
8. Current diagnosis or history of drug or alcohol abuse (DSM-V-TR criteria) within 12 months prior to screening visit.
9. Current primary psychiatric diagnosis of uncontrolled acute psychotic disorder or primary psychiatric diagnoses of bipolar disorder, schizophrenia, obsessive compulsive disorder or currently experiencing a major depressive episode with psychotic features per Diagnostic and Statistical Manual of Mental Disorders Fourth Edition, Text Revision (DSM-V-TR).
10. Currently experiencing or any known history of psychosis (e.g., troublesome hallucinations with or without insight) or delusions within 3 months prior to Screening.
11. A Mini-Mental State Examination (MMSE) score of < 24 or significant cognitive impairment that, in the opinion of the Investigator, could impact the subject's ability to participate in the trial.

Diagnosis and Main Criteria for Inclusion/Exclusion (Continued):

Main Exclusion (Continued):

12. Serum glutamic-oxaloacetic transaminase (AST) or serum glutamic-pyruvic transaminase (ALT) $3 \times$ the upper limit of normal (ULN), or any abnormal laboratory value that is considered clinically significant by the Investigator or could interfere with safety assessments.
13. Current evidence of clinically significant hematological, autoimmune, endocrine, cardiovascular, renal or gastrointestinal disorder that would possibly interfere with the subject's participation in the study (e.g., treated and controlled stable hypertension would not be considered an Exclusion).
14. Subject has current or a history of gastrointestinal, liver, kidney or other condition which may interfere with the absorption, distribution, metabolism or excretion of the study drug (e.g., gastric or intestinal surgery).
15. Any malignant disease other than carcinoma in situ of the cervix or basal cell carcinoma of the skin within the past five years prior to Screening. Subjects with prostate cancer or completely excised squamous cell carcinoma of the skin without reoccurrence within two years prior to Screening may be permitted to enroll following Investigator and study designated physician discussion and documentation of approval. No history of antineoplastic and immunosuppressants administered for cancer treatment (within last 5 years). Note: Biopsy and diagnosis must be completed for any suspicious lesion at dermatology or physical exam.
16. A planned surgical procedure scheduled when the subject would be participating in this study. Subject may subsequently be considered for the study following full recuperation from the surgical procedure.
17. Exposure to any investigational drug within 30 days prior to Screening.
18. Previous enrollment in this study, any other LCIG study or any prior exposure to LCIG.
19. Current enrollment in another clinical study.
20. Subject for whom the placement of a PEG-J tube for LCIG treatment is contraindicated or is considered a high risk for the PEG-J procedure according to the gastroenterology evaluation.
21. Subject has significant current suicidal ideation within one year prior to Screening as evidenced by answering "yes" to questions 4 or 5 on the suicidal ideation portion of the Columbia-Suicide Severity Rating Scale (C-SSRS) completed at Screening or a history of suicidal attempts within the last 2 years.
22. A low B₁₂ level or low-normal B₁₂ level (less than 300 pg/mL) with elevated methylmalonic acid (MMA) at Screening Visit 1.*
23. Positive screen for drugs of abuse or medical marijuana at Screening Visit 1.
24. Consideration by the investigator, for any reason, that the subject is an unsuitable candidate to receive LCIG.
25. Female subject who is pregnant, breastfeeding or is considering becoming pregnant during the study or for approximately 30 days after the last dose of study drug.
26. Male subject who is considering fathering a child or donating sperm during the study or for approximately 30 days after the last dose of study drug.

* If treated and repeat labs confirm levels rise above 300 pg/mL, subject is eligible to re-screen.

Investigational Products:	
Levodopa (20 mg/mL) and Carbidopa monohydrate (5 mg/mL) in an aqueous intestinal gel (carboxymethylcellulose) dispensed in a medication cassette reservoir of 100 mL.
 
Devices are listed below but are not limited to:

Devices in LCIG System	
Description	Manufacturer
Pump CADD Legacy 1400	Smiths Medical
NJ Tube	AbbVie or Covidien
Safety Adapter	Vygon
Extension Tube FR	Vygon
PEG Tube	AbbVie
Intestinal Tube	AbbVie
Y-Adapter for PEG Tube	AbbVie
Click Adapter for PEG Tube	AbbVie
Doses:	
LCIG: For those randomized to LCIG, each subject's dose will be individually optimized in accordance with the LCIG approved product label for countries participating in the study. The dose should be adjusted to an optimal clinical response for the individual patient, which means maximizing the functional ON-time during the day by minimizing the number and duration of OFF episodes (bradykinesia) and minimizing ON-time with disabling dyskinesia.
 
Once optimized, dose adjustments to LCIG can be made up to Day 28. After Day 28 the dose should remain stable for the duration of the study unless adjustments are absolutely needed for safety reasons. If modifications are needed, this should first be discussed with the medical monitor.
 
The total daily dose of LCIG will be composed of three components: (i) the morning dose, (ii) continuous maintenance infusion dose and (iii) extra doses. The continuous infusion is expected to run over a period of 16 consecutive hours each day.

Mode of Administration:	LCIG is dispensed in a medication cassette reservoir of 100 mL, designed to be connected to a portable subject-operated pump for infusion via NJ or PEG-J.
Reference Therapy:	Optimized Medical Treatment
Doses:	PI discretion and/or in accordance with approved product label of the prescribed medications
Mode of Administration:	Oral, sub-lingual or transdermal
Duration of Treatment:	26 weeks

Criteria for Evaluation:

Efficacy:

There will be two alternative primary efficacy variables.

- Change from baseline to Week 26 in NMSS total score
- Change from baseline to Week 26 in PDSS-2 total score

Key secondary endpoints will consist of the following validated scales:

- PDQ-8 summary index
- CGI-C
- UPDRS Part II score

Health Outcome will be assessed by the following measurements that are part of the secondary endpoints:

- PDQ-8
- CGI-C
- UPDRS Parts I and II
- PGIC
- PAS
- GDS-15
- King's PD Pain Scale

Safety:

Safety and tolerability over the course of the study will be assessed by the following measurements:

- Adverse event monitoring
- Neurological exams
- Clinical laboratory evaluations
- Electrocardiogram
- Vital signs and weight
- C-SSRS
- MIDI
- SAQ

Statistical Methods:

Efficacy:

Efficacy Dataset and Treatment Period

The efficacy analysis will be performed on the intent-to-treat dataset which will include all subjects who are randomized to the optimized medical treatment, and all subjects who are randomized to LCIG and received at least one dose of study drug. For assessments of efficacy the treatment period will begin the day after randomization (V3) for subjects randomized to OMT, and the day of first LCIG infusion following PEG-J placement for subjects randomized to LCIG treatment. The treatment period will end on the day of the final visit for subjects randomized to OMT, and on the last day of LCIG study drug infusion for subjects randomized to LCIG treatment. The last assessment prior to randomization will be considered baseline and the last assessment that is no more than 2 days after the end of the treatment period will be considered the final evaluation.

Statistical Methods (Continued):

Efficacy (Continued):

Primary Efficacy Analysis

There are 2 alternative primary efficacy variables, change from baseline to Week 26 for NMSS total score and change from baseline to Week 26 for PDSS-2 total score. Either variable considered statistically significant after multiplicity adjustment is sufficient to declare success of the study.

The primary efficacy analysis model is a likelihood-based mixed-effects model repeated measures (MMRM) analysis of the change from baseline for each post-baseline observation using all observed data. The model will include fixed, categorical effects for treatment, site, visit, and treatment-by-visit interaction, with continuous fixed covariates for baseline score and the baseline score-by-visit interaction. The primary comparison will be the contrast between LCIG and optimized oral treatment at the Week 26 Visit.

The two-sided P values obtained from the MMRM model for NMSS total score change from baseline to Week 26 and PDSS-2 total score change from baseline to Week 26 will be adjusted for multiplicity using the Hochberg procedure. This method controls the family-wise error rate (FWER) at a pre-specified significance level ($\alpha = 0.05$). Specifically, the following steps will be followed:

- If the larger of the 2 P values is ≤ 0.05 (i.e., both P values are ≤ 0.05), both endpoints are considered statistically significant.
- If the larger of the 2 P values is > 0.05 , then compare the smaller P value with 0.025. The second endpoint is statistically significant if the P value is ≤ 0.025 ; otherwise, neither endpoint is considered statistically significant.

Secondary Efficacy Analyses

There are 3 key secondary endpoints:

- PDQ-8 summary index
- CGI-C
- UPDRS Part II score

The key secondary efficacy endpoints will be analyzed with the same MMRM model as the primary efficacy variables. For CGI-C, the scores collected at the visits will be the dependent variable.

If both primary efficacy variables are statistically significant after adjusting for multiplicity, the Stepwise Gatekeeping Procedure will be utilized and the 3 key secondary endpoints will be tested using the Hochberg procedure with significance level of 0.05.

Other secondary endpoints below will be analyzed with the same MMRM model as the primary efficacy variables:

- NMSS domain scores
- PDSS-2 domain scores
- UPDRS total score, Part I score, Part III score, Part IV score
- PGIC
- Parkinson Anxiety Scale (PAS) total and subscale scores
- Geriatric Depression Scale (GDS-15) score

For the analysis on PGIC, the scores collected at the visits will be the dependent variable.

Statistical Methods (Continued):

Safety:

Safety Dataset and Treatment Period

All safety analyses will be performed on the safety dataset which will include all subjects who are randomized to the optimized medical treatment, and all subjects who are randomized to LCIG and received at least one dose of study drug. The treatment period for safety is the same as what is defined for efficacy.

Safety Analyses

Safety analyses will include summaries of adverse events, device-related product complaints, vital signs and special labs.

Determination of Sample Size

Approximately 88 subjects will be enrolled into the study and randomized in a 1:1 ratio to either OMT or LCIG. There are no results on NMSS or PDSS-2 available from randomized trials comparing LCIG and OMT. Interim data from ongoing Phase 3b Study M12-920 showed that the improvement in NMSS total score from baseline to Week 12 is 24.8 in the LCIG arm with standard deviation of 24. Results from Zibetti et al (2013) showed that the improvement in PDSS-2 total score after an average of 3.5 months of LCIG treatment was 13.1. The standard deviation was not provided and is estimated to be 12.2 assuming the correlation between baseline and follow-up visits is 0.5.

The significance level for this study is 0.05. For sample size determination, it is assumed that the improvement in the OMT group is 33% of the LCIG group, i.e., the improvement is 8.2 on NMSS total score and 4.3 on PDSS-2 total score, and that the correlation between these 2 measures is 0.5. Simulation showed that a study with 37 subjects per group will have 90% power to declare statistical significance on at least one of these 2 alternative primary endpoints after multiplicity adjustment using Hochberg procedure. It is further assumed that 10% of randomized subjects in either treatment group will not provide post-randomization efficacy assessment. Additional simulations showed that 44 subjects per group will provide 90% power in the sensitivity analysis using baseline observation carried forward for subjects without post-randomization assessment. Therefore the total planned enrollment is decided to be 88 subjects.

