6.4 Analysis by Planned Visit

A midpoint convention will be used to assign all observations to a planned visit based on the Study Day of the observation. If there are multiple observations on the same day, the average will be taken and considered the observation for the day. If more than one observation is assigned to a planned visit, the last observation will be selected and considered the observation for the planned visit.

The following Study Day windows will be used to assign efficacy and health outcome assessments to planned study visits during 26-week randomized treatment period.

Table 1. Analysis Windows for Efficacy Variables

Assessment	Planned Visit	Nominal Study Day	Study Day Range ^a
NMSS, PDSS-2, PDQ-8, PAS, GDS-15, UPDRS and King's PD Pain Scale	Baseline		≤ date of randomization
	Week 6	42	2 – 63
	Week 12	84	64 – 133
	Week 26	182	134 – 222
CGI-C and PGIC	Week 26	182	≥ 2

a. For subjects in LCIG group, all post-baseline assessments must also be after start of LCIG infusion through PEG-J and no more than 1 day after the date of the last LCIG infusion in the 26-week Treatment Period.

The following Study Day windows will be used to assign safety assessments to planned study visits.

Table 2. Analysis Windows for Safety Variables During the 26-Week Treatment Period

Assessment	Planned Visit	Nominal Study Day	Study Day Range ^a
Vital signs and weight	Baseline		≤ date of randomization
	Week 2	14	2 – 28
	Week 6	42	29 – 63
	Week 12	84	64 – 133
	Week 26	182	134 – 186
	Week 27 FU ^b	189	187 – 301
Clinical labs and Electrocardiograms	Baseline		≤ date of randomization
	Week 12	84	2 – 133
	Week 26	182	> 133
Special labs	Baseline		≤ date of randomization
	Week 12	84	2 – 133
	Week 26	182	134 – 231

- a. For subjects in LCIG group, all post-baseline assessments must also be no more than 1 day after the final PEG-J removal for subjects who have their study device removed after their last infusion of Study M12-927 LCIG.
- b. Applicable only to LCIG subjects who will not transition to commercial LCIG and have study device removed.

The following Study Day windows for Extension Period will be used to assign safety assessments to planned study visits for LCIG subject entering Extension Period.

Table 3. Analysis Windows for Safety Variables During the Extension/Transition Period for the LCIG Group

Assessment	Planned Visit	Nominal Study Day	Study Day Range ^a

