10.2.2 Adverse Event Incidence

The number and percentage of subjects experiencing one or more adverse events in the following adverse event categories during the 26-week Treatment Period will be summarized for each treatment group and for overall subjects by primary SOC and PT.

- Any TEAE
- Any serious TEAE
- Any TEAE that led to discontinuation of study drug

The percentage of subjects in the LCIG group and in the OMT group will be compared using Fisher's exact test. Only P values ≤ 0.100 when rounded to three digits will be presented.

The number and percentage of subjects experiencing one or more adverse events in the following adverse event categories during the Extension/Transition Period will be summarized for OMT/LCIG subjects who enter the Extension/Transition Period by primary SOC and PT.

- Any TEAE
- Any serious TEAE
- Any TEAE that led to discontinuation of study drug

The number and percentage of subjects experiencing one or more TEAEs during the 26-week Treatment Period will also be summarized for each treatment group and for overall subjects by maximum severity category (mild, moderate, severe, or unknown) and primary SOC and PT. Subjects reporting more than one TEAE for a given PT will be counted only once for that term in the most severe category reported. If a subject has an adverse event with unknown severity, then the subject will be counted in the severity category of "unknown," even if the subject has another occurrence of the same event with a severity present. The only exception is if the subject has another occurrence of the same

adverse event with the most extreme severity – "Severe." In this case, the subject will be counted under the "Severe" category.

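### SAP 6.4 keeps the last value in each window, so optional values from the LCIG-only supply visits at Weeks 17 and 22 can be reported as Week 12 or Week 26 in the between-arm safety tables

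*Protocol*

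**What the plan says.** The Protocol synopsis (Methodology) says the OMT group follows the LCIG schedule "except for visits related to NJ/PEG procedures and titration of LCIG". OMT visits fall at the end of Weeks 2, 6, 12 and 26.

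The same synopsis, under LCIG Group, then adds contacts that neither exception covers: "The drug dispensing visits will occur at Weeks 17 and 22", each with a ± 7 day allowance, for return and supply of cassettes. The subject, the caregiver or both may come, to the clinic or the pharmacy. It continues: "Other assessments may be completed during these visits if required". Protocol 5.1.2.2 (Drug Dispensing Visits) repeats this. Neither place says which assessments are meant.

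SAP 6.4 assigns all observations to planned visits by study day, using midpoints between nominal days, and then states: "If more than one observation is assigned to a planned visit, the last observation will be selected". The rule does not ask whether the value came from the scheduled visit. SAP 10.3.1, 10.4.1 and 10.5.1 compare mean changes between arms by ANOVA, with confidence intervals and P values, for laboratory tests, for vital signs and weight, and for ECG. They cover each planned visit and the minimum, maximum and final value.

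**The concern.** Between Weeks 12 and 26 one arm has two scheduled occasions on which extra values may be taken, and the other has none. If those values take over the Week 12 or Week 26 label, a by-visit table sets some LCIG values from about Week 17 against OMT values from Week 12. Nothing in the table would show this. The affected variables include weight and the vitamin panel. These bear on weight loss and polyneuropathy, two of the adverse events of special interest in Protocol 6.1.1.3. The additional sampling in one arm also gives that arm more chances of an extreme minimum or maximum.

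**Working it through.** **Inputs.** Nominal days and windows are from SAP 6.4, Tables 1 and 2. The ± 7 day allowance for visits from Week 6 onward is from Protocol 5.3.1. The supply visits are from the Protocol synopsis and 5.1.2.2.

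**Reproducing the SAP windows.** (42 + 84)/2 = 63 and (84 + 182)/2 = 133, so Week 12 runs from Day 64 to Day 133, as stated for vital signs, weight and the efficacy scales. For laboratory tests, special laboratory tests and ECG, Week 12 is the first post-baseline visit and its window is Days 2–133. For vital signs and weight, the Week 26 window ends near the midpoint with the Week 27 follow-up: (182 + 189)/2 = 185.5, given as Day 186.

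**Placing the visits** (day = 7 × week, ± 7):

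| Visit | Days | Window it falls in |
|---|---|---|
| Week 12 | 84 ± 7 = 77–91 | Week 12 |
| Week 17, LCIG only | 119 ± 7 = 112–126 | Week 12, entirely |
| Week 22, LCIG only | 154 ± 7 = 147–161 | Week 26, entirely |
| Week 26 | 182 ± 7 = 175–189 | Week 26; for vital signs and weight only up to Day 186 |

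**Week 17.** The earliest Week 17 day (112) is later than the latest permitted Week 12 day (91). Under the last-observation rule the Week 17 value always wins. It is 112 − 84 = 28 to 126 − 84 = 42 days past the nominal day.

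**Week 22.** A Week 26 value inside the window is later and supersedes it. Without one, the Week 22 value becomes Week 26, at 182 − 161 = 21 to 182 − 147 = 35 days before the nominal day.

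**Vital signs and weight at Week 26.** A visit on Days 187–189 is allowed by the protocol but lies outside Days 134–186. Its values leave the Week 26 row in either arm. In LCIG a Week 22 value, if taken, then fills the row; OMT has no such visit. Laboratory tests and ECG (after Day 133) and special laboratory tests (134–231) do not have this gap.

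**Sensitivity to the day count.** The synopsis counts LCIG visits from PEG-J placement; the SAP counts study days from the first tube, NJ or PEG-J. After an NJ phase of 7 days, the limit in Protocol 5.3.1.1, Week 17 is Days 119–133 and Week 22 is Days 154–168, so both stay in the same windows. An on-target Week 26 visit would then be Day 182 + 7 = 189, already outside the vital-sign window.

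**Size.** The documents do not give the share p of LCIG subjects with such values. If d is their mean difference between the Week 17 and Week 12 values, the LCIG Week 12 mean moves by p × d. Assuming p between 10% and 30% purely for illustration, that is 0.10 × 44 = 4.4 to 0.30 × 44 = 13.2, or about 4 to 13 subjects. The arm mean would move by 10% to 30% of d. The documents give no d for any safety variable, so the bias cannot be computed.

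**The case against.** The strongest reply is that these are cassette pick-ups. A caregiver alone may attend, at a pharmacy, and then no value arises. The wording permits assessments; it does not schedule any. This stands, and it limits how often the problem can occur.

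The last-in-window rule is the same in both arms, and an unscheduled OMT value would be treated identically. This also stands: what is one-sided is the scheduled opportunity, not the rule. Last versus closest value is a choice of convention, but the chosen one performs poorly when one arm has a visit late in another visit's window.

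An on-time Week 26 value supersedes Week 22, and Protocol 5.4.1 asks for discontinuation assessments from those who leave after PEG-J placement has begun. That holds except for vital signs and weight on Days 187–189.

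Three stronger readings are tempting, and the documents do not support them:

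- **That the primary result is exposed.** The Table 1 efficacy windows would capture a scale score taken at Week 17 or 22. However, blinded central raters give NMSS and PDSS-2 at baseline and Weeks 6, 12 and 26 (Protocol 5.3.1.2), no other scale is scheduled at the supply visits, and the primary contrast is at Week 26.
- **That the adverse-event comparison mainly measures contact frequency.** SAP 10.2.2 says: "The percentage of subjects in the LCIG group and in the OMT group will be compared using" Fisher's exact test. But SAP 10.2 defines treatment-emergent events by when they begin or worsen and counts each subject once per term. Protocol 6.1.4 collects events whether solicited or spontaneous. An OMT event at Week 18 can still be recorded at Week 26.
- **That the synopsis hides the asymmetry.** It discloses the supply visits shortly after the sentence about equal schedules. The mismatch is editorial.

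**Conclusion.** The point holds for the windowing rule. Any optional vital sign, weight, laboratory or ECG value from the Week 17 visit displaces the true Week 12 value. A Week 22 value can stand as Week 26 when no later value is in the window; for vital signs and weight this includes permitted Week 26 visits on Days 187–189. Week 22 cannot displace Week 12.

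The consequence is confined to by-visit and minimum/maximum between-arm safety tables. The primary Week 26 contrast is not directly affected, and no sample-size figure changes. The mapping rests only on stated days and windows. Its practical size depends on how often such values are taken, which the documents do not say. The rule is worth correcting because it mislabels data in one arm and costs little to change.

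**What to change.** **SAP 6.4.** Replace the last-observation rule: when several values fall in one window, use the value from the scheduled visit, identified by its visit label. Otherwise use the value closest to the nominal day. State that a visit labelled Week 26 within its permitted ± 7 days counts as Week 26 even after Day 186, in both arms.

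**Week 17 and 22 values.** Keep them out of the by-visit between-arm tables in SAP 10.3.1, 10.4.1 and 10.5.1, and retain them in listings. Base the between-arm comparison of minimum and maximum on visits scheduled in both arms, since extra sampling in one arm also shifts extremes.

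**Protocol synopsis.** Add drug-supply visits to the exceptions in the sentence on equal schedules, and state which assessments may be done there.

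**Cost.** One SAP rule with matching programming, and one short synopsis correction. No new data, visits or calls to OMT subjects are needed. A few later values are no longer used as visit values.
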